Sub-study 3 TMS visits. During the TMS visits, subjects will first be prepped for the procedure. Shock, and physiology electrodes will be attached (See below for details). Subjects will undergo the shock workup and startle habituation procedures. Next subjects will undergo motor threshold testing to determine the proper TMS dose (Visit 1). Afterward the subjects will undergo the NPU task pre and post delivery of offline rTMS. The procedure of the TMS visits will be identical with the following 2 exceptions. First, the motor threshold testing only needs to be completed once, so this will take place on the first but not the second TMS visit. Second, the subject will receive active stimulation during 1 TMS visit will and sham TMS during another visit. The order of the visits will be counterbalanced across subjects.

b. Recruitment

Participants will be recruited under the screening protocol 01-M-0254: “The Evaluation of Patients with Mood and Anxiety Disorders and Healthy Volunteers.” All recruitment materials (paper or web ads, flyers and listserv announcements) will be IRB approved under this protocol prior to use.

IRB-approved advertisements may be placed in local print and online publications of newspapers, magazines and support or health care organizations, they may include the Washington Post, Express, Washington Parent, Washingtonian, Bethesda Magazine, Washington Examiner, Military papers, NAMI Advocate, campus newspapers, the NIH Record/CC News, and the AADA. Web ads will direct readers to the study specific link on the NIMH Join a Study website.

Notecards and/or flyers may be posted on bulletin boards at local establishments including grocery stores, coffee shops, community centers, college campuses, NIH Clinical Center, libraries, or placed in advocacy group offices or in doctor’s office waiting rooms with approval of the venue or in accord with their policy. They may be made available at outreach exhibits, speaking engagements, and professional meetings

with approval of the venue or in accordance with their policy. Clinicians who are contacted will be provided with information to disseminate to patients as they see fit. We will explain to them that individuals interested in participating in our studies will need to initiate contact with our group and that we will not make this initial contact. Notecards and/or flyers may be given directly to those requesting study information.

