There will be 4, 14 min runs of the experiment (2 active and 2 sham). Within each run, there will be 8 blocks (2 predictable, 2 unpredictable, 4 neutral). There are twice the number of neutral blocks to ensure that safe blocks alternate with threat (predictable or unpredictable) blocks. During half of the blocks (1 predictable, 1 unpredictable, 2 neutral), subjects will receive a continuous train of 1 Hz stimulation to the left IPS. Within each block, there will be 2 types of trials based on the delivery of startle probes. Startle probes will be presented either during the cue period, or the ITI. During the predictable and unpredictable blocks, there will be 4 trials per condition. Given that there will be twice as many neutral blocks, during these blocks there will only be 1 trial per condition. The result will be a total of 192 trials across the entire experiment (2 [active vs. sham] x 2 [neutral vs. predictable vs. unpredictable] x 2 [maintenance vs. ITI] x 2 [TMS vs. no TMS] x 2 [run repetitions] x 4 [block*trial repetitions]). Trials will last approximately 17 seconds. There will be a total of 3 shocks per run presented during either the ITI (unpredictable) or cue (predictable) periods.

Sub-study 3, NPU task: There will be 1 pre-TMS and 1 post-TMS NPU run during each TMS visit. Within each run, there will be 8 blocks (2 predictable, 2 unpredictable, 4 neutral). There are twice the number of neutral blocks to ensure that safe blocks alternate

with threat (predictable or unpredictable) blocks. Startle probes will be presented either during the cue period, or the ITI. During the predictable and unpredictable blocks, there will be 2 trials per condition. Given that there will be twice as many neutral blocks, during these blocks there will only be 1 trial per condition. The result will be a total of 192 trials across the entire experiment (2 [active vs. sham] x 3 [neutral vs. predictable vs. unpredictable] x 2 [maintenance vs. ITI] x 2 [pre-TMS vs. post-TMS] x 8 [block*trial repetitions]). There will be a total of 3 shocks per run presented during either the ITI (unpredictable) or cue (predictable) periods.

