Subjects will be informed that they can withdraw from the study whenever they wish. Sample shocks will be administered prior to the study. At this point, subjects will be explicitly asked if they wish to continue. Subjects receiving the frontal TMS will also be given a chance to experience the sensation of the TMS via electric scalp stimulation. Subjects will be given the opportunity to discontinue after this sensation screen. The experiment will also be stopped for any subject who exhibits signs of distress during any phase of the study. Subjects will be constantly monitored via closed circuit video by the AI for MRI sessions. An AI is present during TMS sessions. A credentialed staff member (RN, NP or MD) will assess the subject at the conclusion of the study or at any time if significant side effects develop. The subject will be withdrawn at any time if unable to follow the rules for participation in this study.

9. Outcome Measures

a. Primary outcome measures

The primary outcome measures will be APS reduction as a function of stimulation type, active or sham stimulation.

10. Statistical Analysis

a. Analysis of data/ study outcomes

Sternberg. APS scores will be created by subtracting the startle magnitude during the safe blocks from the startle magnitude during the threat blocks. These scores will be analyzed using a 2 [block: active vs. sham] x 2 [stimulation: TMS vs. no TMS] x 2 [interval: maintenance vs. ITI] repeated measures ANOVA.

NPU. APS scores for the cue and ITI will be created by subtracting the startle magnitude during the safe blocks from the startle magnitude during the unpredictable blocks. FPS scores will be calculated by subtracting the startle magnitude during the predictable ITI from the startle magnitude from the predictable cue. These scores (APS cue, APS ITI, FPS cue) will be analyzed using a 2 [block: active vs. sham] x 2 [stimulation: TMS vs. no TMS] repeated measures ANOVA.

b. Power analysis

In our Sternberg pilot experiment, we obtained the effect size ($f=0.72$) for our observed WM load-related decrease in anxiety. Assuming a somewhat smaller effect size ($f=0.5$) due to regression to the mean, if we set power at .95 and experiment-wise, two-tailed alpha at 0.05. Based on these parameters, we will need 48 subjects per experiment. Assuming a 15% unusable data rate and 3 subjects to initially adjust the experimental procedure, we will need 58 subjects per experiment.

11. Human Subjects Protection

a. Subject selection

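### Sub-study 3 collects a pre-TMS run at each visit, but the only NPU model in section 10.a cannot use it as a covariate, so precision is lost unless the pre and post differences are highly correlated

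*Combined protocol and SAP*

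**What the plan says.** Section 9.a defines the primary outcome: "The primary outcome measures will be APS reduction as a function of stimulation type, active or sham stimulation". In section 10.a each of the three NPU scores, two for APS (at the cue and in the ITI) and one for FPS, goes into an ANOVA with within-subject factors "2 [block: active vs. sham] x 2 [stimulation: TMS vs. no TMS". The Sternberg scores get a "2 [block: active vs. sham] x 2 [stimulation: TMS vs. no TMS] x 2 [interval: maintenance vs. ITI] repeated measures ANOVA". Neither model has a covariate or a planned simple contrast, and no ANOVA term is named as the test of the primary outcome. Section 10 has no separate model for sub-study 3.

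For sub-study 3, section 4.a says: "Afterward the subjects will undergo the NPU task pre and post delivery of offline rTMS". There are two TMS visits per subject, one active and one sham, in counterbalanced order. Section 4.d confirms one pre-TMS and one post-TMS NPU run per visit and lists pre vs post as a design factor.

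Sub-studies 1 and 2 are different. Each subject has two active and two sham runs, and within each run it is only in half the blocks that "subjects will receive a continuous train of 1 Hz stimulation to the left IPS" (section 4.d). Section 4.a mentions random intervals and a random selection of trials. Neither section states how active and sham runs are ordered or balanced, or gives a washout between stimulated and unstimulated blocks.

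**The concern.** In sub-study 3 the pre-TMS run is measured before that visit's stimulation, so it is a baseline. An ANOVA that takes it as the second level of a two-level factor offers two terms involving active vs sham, and both fix its weight in advance. The main effect averages the baseline with the outcome and so dilutes the effect. The interaction subtracts the baseline at full weight, which is optimal only if the regression of the post difference on the pre difference has slope 1. With similar variances and imperfect correlation that slope is below 1, and the excess weight adds noise. With 48 completers fixed, the cost is power and interval width. It is not bias.

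**Working it through.** **Inputs.** Completers per experiment 48, assumed effect size f = 0.5, and "if we set power at .95 and experiment-wise, two-tailed alpha at 0.05" (section 10.b). Rho is not given, so a range is shown.

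**The plan's own figure.** Reading f = 0.5 as a standardised within-subject difference of 0.5 on a one-degree-of-freedom contrast (my assumption), the normal approximation gives ((1.960 + 1.645)/0.5)² = 52. The exact t calculation gives 54, and 48 subjects give 92.4% power. The stated 48 for 95% is therefore not reproduced on this reading. That is a separate matter; I keep 48 and 0.5 as the common anchor.

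**Set-up for sub-study 3.** Let D1 be post-TMS APS at the active visit minus post-TMS APS at the sham visit, and D0 the same difference pre-TMS. Assume Var(D1) = Var(D0) = V, correlation rho, E(D1) = delta and E(D0) = 0.

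- Main effect, (D1 + D0)/2: mean delta/2, variance V(1 + rho)/2. Rescaled to estimate delta, the variance is 2V(1 + rho).
- Interaction, D1 − D0: mean delta, variance 2V(1 − rho).
- Adjusted, D1 given D0: mean delta, variance V(1 − rho²).

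The ratios to the adjusted variance are:

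- interaction: 2(1 − rho)/[(1 − rho)(1 + rho)] = 2/(1 + rho)
- main effect: 2(1 + rho)/[(1 − rho)(1 + rho)] = 2/(1 − rho)

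**Example at rho = 0.3.** The noncentrality for D1 alone is 0.5 × √48 = 3.464. Interaction: 3.464/√1.4 = 2.93, power 82%. Adjusted: 3.464/√0.91 = 3.63, power 94%. Main effect: 3.464/√2.6 = 2.15, power 56%.

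| rho | Interaction variance ÷ adjusted | Main effect variance ÷ adjusted | Power: main | Power: interaction | Power: adjusted |
|---|---|---|---|---|---|
| 0 | 2.00 | 2.00 | 67% | 67% | 92% |
| 0.3 | 1.54 | 2.86 | 56% | 82% | 94% |
| 0.5 | 1.33 | 4.00 | 50% | 92% | 97% |
| 0.7 | 1.18 | 6.67 | 45% | 99% | >99% |
| 0.8 | 1.11 | 10.0 | 43% | >99% | >99% |

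Power is two-sided at 0.05 with n = 48; the adjusted column allows for the slope and order term (45 rather than 47 degrees of freedom). Simulation with 20,000 replicates agreed to within about one percentage point. The adjusted test kept its 5% level under the null and its estimate was unbiased.

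**Sub-studies 1 and 2, same algebra with the assumptions relaxed.** D1 and D0 are now the differences in TMS and no-TMS blocks.

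- *Additive shift between active and sham runs.* With no true effect and a shift of 0.3 SD in both D1 and D0, the interaction cancels it and stays at 5%. The adjusted contrast keeps (1 − rho) × 0.3 SD, that is 0.30, 0.21 and 0.15 SD at rho 0, 0.3 and 0.5. Its type I error is about 49, 29 and 20%.
- *Carry-over into unstimulated blocks.* With half the effect carried over and a standardised effect of 0.5, power for main / interaction / TMS blocks alone / adjusted is 91 / 27 / 93 / 85% at rho 0.2 and 84 / 40 / 92 / 80% at rho 0.5. The adjusted estimate falls to 0.45 and 0.38, and the interaction estimate to 0.25.

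**The case against.** The interaction is a standard and valid difference-in-differences. It uses every pre-TMS observation, matches the post-TMS contrast alone at rho 0.5, beats it above that, and at rho 0.8 has only 11% more variance than the adjusted contrast. If rho is high, little is gained. That stands, and is why the loss has to be given as a range. It does not help the main effect, which is the worse of the two terms throughout this range once rho is above 0.

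It can also be said that section 10.a never states how sub-study 3 will be analysed, so the criticism is of an inferred model. That is fair as far as it goes. But the 2×2 is the only NPU model in the plan, and the pre/post structure maps directly onto its no-TMS/TMS factor.

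A reader might infer something stronger: that in all three sub-studies the ANOVA discards the unstimulated data and should be replaced by the adjusted contrast. The documents do not support that. The interaction does not discard those data. At rho near 0 they hold almost no information to discard, and the loss comes from weighting them. In sub-studies 1 and 2 the unstimulated blocks share a run with the 1 Hz trains and run-order balance is not stated, so they cannot be assumed to be a baseline. A run shift inflates the adjusted test's error rate, and an order term cannot repair this if every subject has the same run order. With 50% carry-over the adjusted contrast also has less power than the main effect at the rho values shown.

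**Conclusion.** The point holds for sub-study 3, as a matter of efficiency and not of validity. Neither active-vs-sham term in the 2×2 is as precise as a baseline-adjusted contrast from the same data. The interaction's variance is 2.0 to 1.11 times the adjusted variance over rho 0 to 0.8, and the main effect tests only half of delta. With a standardised effect of 0.5 and 48 completers, adjusting rather than using the interaction gains 25 percentage points of power at rho 0, 12 at rho 0.3, 5 at rho 0.5 and almost nothing from rho 0.7.

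This rests on equal variances, an effect present only in the post-TMS run, counterbalanced visits as stated, and no effect of the first visit's stimulation lasting about a week into the second visit's pre-TMS run. For sub-studies 1 and 2 the adjusted contrast trades robustness for precision, and the documents give no grounds for making it the main test.

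**What to change.** **Sub-study 3.** Add a model to section 10.a. For each subject take the post-TMS APS difference, active minus sham visit. Regress it on the same pre-TMS difference, left uncentred, and on visit order coded −½/+½. The intercept, at zero pre-TMS difference and averaged over the two orders, is the active-vs-sham effect. Apply the same model to APS cue, APS ITI and FPS cue, using the FPS difference for the last. Keep the 2×2 interaction as a sensitivity analysis.

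**Sub-studies 1 and 2.** Use the interaction for the active-vs-sham test, because it removes any additive shift between active and sham runs. Report the adjusted contrast and the TMS-block-only contrast as sensitivity analyses, under written assumptions of no carry-over and of counterbalanced runs. The TMS-block-only contrast matters because carry-over weakens the interaction. For Sternberg, state whether each contrast is taken within interval or averaged over it.

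**Cost.** For sub-study 3, two degrees of freedom (slope and order) and a short addition to the analysis text, with no new data or subjects. For sub-studies 1 and 2, the run order must also be documented.

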Sternberg Task: Expose subjects to active or sham TMS to a region of the frontoparietal attention network during the Sternberg WM task. Subjects will have to maintain a series of letters in WM for a brief interval during blocks of safety and threat of shock.

NPU Task: Expose subjects to active or sham TMS to a region of the frontoparietal attention network during the NPU threat test. Subjects will be exposed to blocks in which they are either 1) safe from shock (neutral), 2) at risk of shock delivered only during a cue (predictable), or 3) at risk of shock presented randomly (unpredictable).

Outcome measures: In both studies the primary outcome measure will be anxiety-potentiated startle (APS), which is the increase in startle magnitude during periods of threat compared to periods of safety. We expect active, but not sham TMS to increase activity in the dlPFC, and therefore reduce APS in both studies.

Table of Contents

| | |
|---|-----------|
| 1. Introduction and Background | 9 |
| a. Background | 9 |
| b. Significance | 11 |
| c. Preliminary data | 11 |
| 2. Study Objectives | 17 |
| a. Primary objectives | 17 |
| 3. Subjects | 18 |
| a. Description of study populations | 18 |
| b. Inclusion criteria | 18 |
| c. Exclusion criteria | 18 |
| 4. Study Design and Methods | 19 |
| a. Study overview | 19 |
| b. Recruitment | 20 |
| c. Screening | 21 |
| d. Study procedures | 22 |
| e. End of participation | 27 |
| 5. Management of Data and Samples | 27 |
| a. Storage | 27 |
| b. Data sharing plan | 28 |
| 6. Additional Considerations | 28 |
| a. Research with investigational drugs or devices | 28 |
| b. Gene therapy | 28 |
| 7. Risks and Discomforts | 28 |
| a. Procedures | 28 |
| b. Procedures to Minimize Risks | 31 |
| 8. Subject Safety Monitoring | 32 |
| 9. Outcome Measures | 33 |
| a. Primary outcome measures | 33 |
| 10. Statistical Analysis | 33 |
| a. Analysis of data/ study outcomes | 33 |
| b. Power analysis | 33 |
| 11. Human Subjects Protection | 34 |
| a. Subject selection | 34 |
| Justification for exclusion of children | 34 |
| Justification for inclusion of other vulnerable subjects | 34 |
| Justification for exclusion of other vulnerable subjects | 34 |
| Justification for exclusion of non-English speaking subjects | 35 |
| Justification for exclusion of subjects over 50 years of aged | 35 |
| Justification for exclusion of non-right-handed subjects | 35 |

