One variant of the threat of shock paradigm is the so-called NPU paradigm, where subjects are exposed to simple cues during blocks of no threat (N), predictable threat (P), and unpredictable threat (U) (Schmitz and [name], 2012). During this paradigm, simple geometric shapes serve as cues (presented for 8 s). During the predictable threat blocks, these cues indicate that a shock may occur, while during the unpredictable and neutral blocks, these cues are not predictive of the shock. During the no threat blocks subjects are instructed that they are completely safe from shocks, and during the unpredictable blocks, subjects are instructed that they could receive a shock at any point. This paradigm provides measures of fear (e.g., fear-potentiated startle) associated with the threat cue in the P condition and of anxiety (e.g., anxiety-potentiated startle) in the N, P, and U contexts (no-cue periods). This paradigm is ideal to test the top-down inhibition hypothesis because it allows for the testing of both fear and anxiety, without adding additional cognitive demands. In addition, cue presentations during the NPU task activate the dlPFC (See below), which may reflect an implicit form of top-down emotion regulation.

The purpose of this protocol is to use TMS to determine the role of the FPN in anxiety reduction. According to our model, we have 2 hypotheses. First, suppressing activity in

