4. Study Design and Methods

a. Study overview

Sub-studies 1 and 2 will consist of 2 outpatient visits (1 MRI visit, 1 TMS visit), each lasting up to 3 hours each. Sub-study 3 will consist of 3 outpatient visits (1 MRI visit, 2 TMS visits). Healthy volunteers will be assigned to one of the three sub-studies. All visits will be located in the Clinical Center at the NIH in Bethesda, MD. The MRI visit will take place in the NMR center and the TMS visits will take place on the 7th floor inpatient unit. The visits will be separated by ~1 week (no more than 2 weeks), according to the subject's availability. Each participant will sign the consent form during the MRI visit.

MRI visit. The MRI visit will be used to identify single-subject FPN targets for TMS. Subjects participating in multiple sub-studies will complete the MRI visit only when participating in their first sub-study, unless the MRI visit needs to be repeated. First subjects will complete the TMS Adult Safety Screen (TASS) (Keel et al., 2000), to ensure that they meet the inclusionary criteria for TMS. Only subjects eligible for TMS will complete the MRI visit. Subjects in Sub-study 3 will also receive TMS sensation screen. During this screen, subjects will receive a single train of electric scalp stimulation, and asked whether they would be willing to tolerate this level of scalp stimulation during the TMS sessions.

Next, subjects will be setup to go into the MRI scanner. A T1, a T2, and a diffusion weighted echo-planar series will be collected to assist with targeting (Fox, 2009). After, the subject will undergo 1 run of resting state, and 1 run of the Sternberg WM task without shock, to identify single-subject FPN targets for TMS. This visit will be the same for subjects in both sub-studies.

Sub-studies 1 and 2 TMS visit. During the TMS visits, subjects will first be prepped for the procedure. Shock, and physiology electrodes will be attached (See below for details). Subjects will undergo the shock workup and startle habituation procedures. Next subjects will undergo motor threshold testing to determine the proper TMS dose. Afterward the subjects will receive stimulation TMS while completing the task (WM or NPU). Stimulation type will be manipulated within subjects, across trials. Subjects will receive active or sham TMS to the left IPS during random intervals of the NPU task, or during a random selection of WM trials.

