During the TMS visit, the subject will complete a packet of pre-experiment questionnaires. Next the subject will be connected to the equipment. The stimulation device, as well as the electrodes for shock and autonomic measures will be attached, and the subject will be given headphones for the white noise delivery. Subjects will undergo TMS motor threshold testing (during first TMS visit only for sub-study 3). Once the subject is prepped for the experiment, they will undergo startle habituation, and the shock workup. After the shock workup, subjects will complete the task while receiving TMS. Once the task is complete, the subject will complete retrospective questionnaires. For sub-studies 1 and 2, each subject will be assigned to one of two tasks (Sternberg WM or NPU). The TMS visit will be the same for subjects in both sub-studies with the exception of being assigned to one of the two tasks. For sub-study 3, subjects will participate in the NPU task pre and post TMS delivery, which will occur during a run of the Sternberg WM task (for active TMS targeting).

Sub-study 1, Sternberg task: The session will begin with a startle habituation phase with 9 startle stimuli presented alone to reduce startle reactivity. On each WM trial, subjects will see a series of 4 letters presented singularly (encoding period) that will be followed by a brief interval where subjects are required to maintain these letters (maintenance period). At the end of the maintenance period, subjects will be prompted to make a response based on the task instructions (response period; Sternberg, 1966). The response prompt will consist of a letter and a number. The letter will be chosen from the study series, and the number will correspond to a position in the series. The subjects will indicate whether the position of the letter in the series matches the number.

There will be 4, 14 min runs of the experiment (2 active and 2 sham). Within each run, there will be 4 blocks (2 threat, 2 safe). During 1 block each of safe and threat, subjects

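### Sub-study 3's crossover fits the only NPU model only by a reading the plan never states; visit order is in no model, and neither the primary APS score nor the primary ANOVA term is named

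*Combined protocol and SAP*

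**What the plan says.** Section 10.a gives two models, headed by task (Sternberg and NPU) rather than by sub-study. The NPU text defines two APS scores: "APS scores for the cue and ITI will be created by subtracting the startle magnitude during the safe blocks", with startle in the unpredictable blocks as the other term of the difference. It adds one FPS score and then says: "These scores (APS cue, APS ITI, FPS cue) will be analyzed using a 2 [block: active vs. sham] x 2 [stimulation: TMS vs. no TMS". The two factors are active/sham and TMS/no TMS, in a repeated measures ANOVA.

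Section 4.d attaches the TMS/no TMS factor to Sub-study 2, where half of the NPU blocks get a 1 Hz train. For Sub-study 3, the trial count in the same section uses pre-TMS/post-TMS instead. There, "subjects will participate in the NPU task pre and post TMS delivery, which will occur during a run of the Sternberg WM task", so no NPU block has stimulation switched on. Section 4.a places active and sham at separate visits and adds: "The order of the visits will be counterbalanced across subjects".

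Section 9.a defines the primary outcome for the whole protocol in one sentence: "The primary outcome measures will be APS reduction as a function of stimulation type, active or sham stimulation". Section 10.b sets an experiment-wise, two-tailed alpha of 0.05 and 48 completers per experiment.

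**The concern.** Two choices that should be fixed in advance are open for Sub-study 3.

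- **The term.** APS reduction by stimulation type could mean the active/sham x pre/post interaction, or the active/sham main effect over both runs. The second averages in data recorded before any stimulation at that visit.
- **The score.** APS cue and APS ITI are both defined and neither is ranked.

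If either choice can be made after the data are seen, the nominal 5% is not the real error rate. Separately, the design balances visit order, but no model contains it. Any systematic difference between first and second visits then goes into the error term.

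**Working it through.** **Inputs.** From the documents: n = 48 completers, two-sided alpha 0.05 and f = 0.5 (section 10.b). That f is scaled down from a working-memory-load effect (pilot f = 0.72), so the documents give no TMS effect size. They also do not give the correlation between the two APS scores, the size of any visit effect, or rho, the correlation between a subject's pre-TMS and post-TMS active-sham differences. These are assumed below, with ranges.

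**The plan's own figure.** Reading f as a standardised within-subject contrast (dz = 0.5), power at n = 48 is 92.4% two-sided, and 95% power needs 54. The stated 48 is not reproduced on that reading. This is a separate matter; 48 is used below as the planned n.

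**Factors side by side.**

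| | Sub-study 2 | Sub-study 3 | NPU model in 10.a |
|---|---|---|---|
| Active/sham | by run | by visit | yes, labelled block |
| Second factor | TMS on/off by block | pre/post run | TMS/no TMS |
| Visit order | not applicable (one TMS visit) | counterbalanced | absent |

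**Choice of score.** Under the null, with each score tested at 0.05 and either allowed to count (simulated, n = 48): type I error is 9.8%, 9.1%, about 8.4% and 7.0% at correlations 0, 0.5, 0.7 and 0.9. At correlation 0 this agrees with 1 - 0.95^2 = 9.75%.

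**Choice of term.** Let s^2 be the variance of the active-sham difference in one run.
- Interaction (change score): variance 2s^2(1 - rho). With dz = 0.5 fixed here, power is 92%.
- Main effect over both runs: the effect is halved and the variance is s^2(1 + rho)/2, so dz_main = 0.5 x sqrt((1 - rho)/(1 + rho)) = 0.500, 0.367, 0.289, 0.210 at rho 0, 0.3, 0.5, 0.7. Power is 92%, 70%, 50%, 30%. There is no loss at rho 0 and a large one at moderate rho.

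**Visit order omitted.** Suppose the pre-to-post change differs between visits by q, in SD units of the contrast. The contrast then has mean tau + q in one order and tau - q in the other. With 24/24 the q terms cancel in the mean, so there is no bias, but the estimated variance rises from 1 to about 1 + q^2. At q = 0.5 that is 1.25, which inflates the standard error by sqrt(1.25) = 1.12. Simulated type I error is about 2.6% to 2.8% and power 88%. With order in the model (46 df) they are about 5% and 92% to 93%. At q = 0.25 the cost is small: type I error about 4.3%, power about 91.5%. If losses leave orders at 26/22, a bias of (26 - 22)/48 x q = 0.083q appears, or 0.042 SD at q = 0.5.

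**Baseline adjustment.** Regress the post-TMS active-sham difference on the pre-TMS active-sham difference plus order, and test the intercept. The variance is s^2(1 - rho^2), which is (1 + rho)/2 times that of the change score: 0.75 at rho 0.5 and 0.95 at rho 0.9. Power (45 df) is 97% and about 93%, against 92% for the interaction, with dz = 0.5 fixed on the change score. If 0.5 SD is fixed on the post-TMS contrast instead, the interaction has 67%, 92% and about 100% at rho 0, 0.5 and 0.9, and the adjusted test 92%, 97% and about 100%.

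**Carry-over.** Assume a true effect of -0.5 SD and that active stimulation at visit 1 leaves a shift of half that size (-0.25) in both visit-2 runs. The mean active-sham difference then moves by +0.125 in both the pre and the post run. The interaction is post minus pre, so the shift cancels and the estimate stays at -0.50. The adjusted estimate is (-0.5 + 0.125) - rho x 0.125 = -0.375 at rho 0 and -0.4375 at rho 0.5. Simulation gives about -0.37 to -0.38 and -0.44.

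**The case against.** The best defence is that section 10.a is organised by task, Sub-study 3 is an NPU study, and the stated 2 x 2 has the right shape once TMS/no TMS is read as post/pre. Labels are loose elsewhere too: section 4.d calls the NPU cue/ITI factor maintenance/ITI, and section 10.a calls active/sham a block factor although section 4.d assigns it by run. This largely stands. A reader might infer that Sub-study 3 has no applicable model at all; the documents do not support that. The active/sham x pre/post interaction is a natural reading and a valid test. What remains is that the mapping is never stated and that it would still leave visit order out. The Précis sentence "We expect active, but not sham TMS to increase activity in the dlPFC, and therefore reduce APS in both studies" leans towards an interaction, but it speaks of two studies and is weak evidence for the third.

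A reader might also infer that section 9.a names no primary measure. It does name APS, which excludes FPS, and active versus sham. The gap is narrower: the APS score and the ANOVA term. Section 1.a narrows the score further, since it speaks "of anxiety (e.g., anxiety-potentiated startle) in the N, P, and U contexts (no-cue periods", which corresponds to APS ITI, but the analysis section does not adopt that.

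The experiment-wise alpha in section 10.b shows an intention to control error across tests. It stands as intent; no method follows from it.

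Finally, baseline adjustment is a choice made for precision, not a correction of bias, and carry-over weakens it. That stands, and is why it is not put forward below as the default primary test.

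**Conclusion.** The point holds as a gap in specification, not as a flaw in the design or a bias in the stated analysis. For Sub-study 3 the plan leaves open the mapping of its second factor, the primary APS score and the primary term, and it omits visit order.

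The supportable size is a type I error of about 8% to 10% if either APS score may count, at an assumed correlation of 0.7 to 0. Letting either of the two terms count as well would give 16% to 18%. That larger figure should not be attributed to the plan, because it requires the main effect over both runs to be accepted as a test, and that is not the natural reading.

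Omitting order is conservative with balanced orders: about 4 percentage points of power at an assumed visit difference of 0.5 SD, and about 1 point at 0.25 SD. Bias arises only if losses unbalance the orders. All power figures rest on an assumed dz of 0.5, and the gain from baseline adjustment depends on a rho that the documents do not give.

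**What to change.** Before data are seen, give Sub-study 3 its own paragraph in section 10.a.

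1. State that the primary test is the active/sham x pre/post interaction on one named APS score. Section 1.a's no-cue definition points to APS ITI; if APS cue is preferred, say why. Make the other APS score and FPS secondary. State that the active/sham main effect over both runs is not the test.
2. Add visit order, coded +/-0.5, to that model.
3. Report the baseline-adjusted version: post active-sham difference on pre active-sham difference (not mean-centred) plus order, testing the intercept. It may be made primary for precision if carry-over across the roughly one-week gap is judged negligible and the plan says so.

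The cost is one degree of freedom for order (46 instead of 47), or two with baseline as well (45), and no new data.

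Separately, the stimulation target needs reconciling. The Précis and the justification for sensitive procedures in section 11.a describe dlPFC stimulation, while section 4.a says for Sub-studies 1 and 2 "Subjects will receive active or sham TMS to the left IPS during random intervals of the NPU task" (or during selected working-memory trials), and section 4.d agrees with section 4.a. The analysis points above do not depend on it.
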